We will report mean and standard deviation of normally distributed variables and we will compare them using the student T-test. We will report non-normally distributed variables as median and interquartile range, comparing them using the Mann-Whitney U test. Categorical variables will be expressed as proportion and compared using the Chi-square or Fisher exact test as appropriate. We will perform a bivariate analysis to identify variables associated with the composite outcome of major peri-intubation adverse events and significant variables will be then used to construct a multivariate logistic model in order to identify independent variables.

The following planned secondary analyses will be performed:

- Place of intubation: OR vs NORA
- Type of surgery: cardiac vs non-cardiac surgery, ear-nose-throat surgery, thoracic surgery
- Urgency of the procedure: planned advanced airway management vs unplanned advanced airway management
- Type of hypnotic drug used: propofol vs different drug
- Airway management procedure: difficult airway management vs not difficult
- Patient's condition:
 - ASA 1-2 vs ASA 3-4;
 - BMI<30 vs BMI>30;

A two-sided p-value < 0.05 will be considered statistically significant. Statistical analysis will be performed by R 3.6.2 (http://www.R-project.org)

Sample size

Post-intubation hypotension has been reported in up to 10% of patients [11].

We aim to collect data on 1000 major peri-intubation events during anesthesia in order to include at least 10 putative variables associated with this event in planned analyses and sub-analyses, therefore we plan to recruit a total of 10.000 patients. Considering a 5% data lost, our final sample size will be of 10500 patients. We estimated an average number of 50 intubations/week at each centre so we plan to recruit a total number of 210 centres.

CENTRES RECRUITMENT

We will recruit academic and non-academic hospitals worldwide. Any centre that performs advanced airway management in the context of general anesthesia for either surgery or diagnostic/therapeutic procedures will be eligible for participation. Centers characteristics (academic vs non-academic, workload etc.) will be collected.

We will launch a website (www.stargate.com) and a social media channel (@stargate_study) where we will publish study information and documents (e.g. protocol, case report form, national coordinator list) which will be available for potentially interested investigators.

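### Student's t-test is named for normally distributed variables although the planned event comparison is about 1,000 against 9,000 patients; if the pooled form is meant, the 5% level is not protected when SDs differ

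*Protocol*

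**What the plan says.** The synopsis and the Statistical Analysis section of the protocol carry the same text. For normally distributed variables: "We will report mean and standard deviation of normally distributed variables and we will compare them using the student T-test". For the others: "We will report non-normally distributed variables as median and interquartile range, comparing them using the Mann-Whitney U test". The threshold is common to all tests: "A two-sided p-value < 0.05 will be considered statistically significant".

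The next step is a screen: "We will perform a bivariate analysis to identify variables associated with the composite outcome of major peri-intubation adverse events". Variables significant there go on to a multivariable logistic model. No separate test is named for the screen.

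The group sizes follow from the Sample size paragraph: "We aim to collect data on 1000 major peri-intubation events during anesthesia", and "therefore we plan to recruit a total of 10.000 patients" (ten thousand). The software is R 3.6.2. The protocol does not say whether variances are pooled, does not mention Welch, and gives no SD for any variable.

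**The concern.** The two-sample t-test that bears Student's name estimates one common variance from both groups. When the groups are of equal size, unequal SDs do little harm to its level. When one group is nine times the other, the pooled variance is close to that of the larger group, while the variance of the mean difference is dominated by the smaller group. The standard error is then too small if the smaller group is the more variable, and too large if it is the less variable. A larger total does not help, because the error depends on the ratio of the sizes.

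Two uses are at stake. One is the set of descriptive comparisons of patients with and without an event. The other, if the tests listed just before it are the ones used, is the bivariate screen. There a distorted p-value helps decide which variables enter the logistic model.

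**Working it through.** **Inputs from the protocol.** 1,000 events; 10% event rate; 10,000 patients; 5% data loss; 50 patients per centre; two-sided alpha 0.05.

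**Assumed.** The ratio r = SD(event) / SD(no event), tried from 0.8 to 2.0, because the protocol gives no SDs.

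**Step 1: the plan's own figures.**
- 1,000 / 0.10 = 10,000 patients.
- 10,000 × 1.05 = 10,500. Dividing by 0.95 instead gives 10,527, a difference of no importance.
- 10,500 / 50 = 210 centres.

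The stated figures are reproduced. The implied groups are n1 = 1,000 with an event and n0 = 10,000 − 1,000 = 9,000 without.

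**Step 2: actual level of the pooled test.** Set the non-event SD to 1.
- True variance of the mean difference: V = r²/n1 + 1/n0.
- Variance that the pooled test uses, on average: P = [((n1 − 1)r² + (n0 − 1)) / (n1 + n0 − 2)] × (1/n1 + 1/n0).
- q = √(V/P), and actual level = 2 × (1 − Φ(1.96/q)).

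For r = 1.5:
- V = 2.25/1,000 + 1/9,000 = 0.002361.
- P = [(999 × 2.25 + 8,999)/9,998] × 0.001111 = 1.1249 × 0.001111 = 0.001250.
- q = √1.889 = 1.374, so 1.96/q = 1.426 and the level is 15.4%.

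For r = 0.8:
- V = 0.64/1,000 + 1/9,000 = 0.000751.
- P = 0.9640 × 0.001111 = 0.001071.
- q = √0.701 = 0.837, so 1.96/q = 2.341 and the level is 1.9%.

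| r (assumed) | Pooled, formula | Pooled, simulated | Welch, simulated |
|---|---|---|---|
| 0.8 | 1.9% | 1.8% | 4.9% |
| 0.9 | 3.3% | 3.3% | 5.2% |
| 1.0 | 5.0% | 5.1% | 5.1% |
| 1.1 | 6.9% | 6.6% | 4.7% |
| 1.2 | 9.0% | 9.0% | 5.0% |
| 1.5 | 15.4% | 15.5% | 5.0% |
| 2.0 | 24.5% | 24.4% | 4.9% |

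The simulations used 20,000 runs per ratio.

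**Step 3: is the imbalance the cause?** With 5,000 against 5,000 the same formula gives 5.0% at every ratio tried. The distortion therefore comes from the 1:9 split combined with unequal SDs.

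**Step 4: does the screen matter, given that a logistic model follows?** In simulation with equal means, the Wald test of a one-covariate logistic model rejects at the same rate as the pooled t-test: 1.6% against 1.6% at r = 0.8, 8.9% against 8.9% at r = 1.2, and 14.5% against 14.5% at r = 1.5. The model thus shares the distortion. A variable must pass both steps, however, so a Welch screen still limits false entry. The chance that a null variable passes both falls from 9.1% to 5.4% at r = 1.2, and from 14.8% to 4.4% at r = 1.5. At r below 1 the Welch screen restores its own level, but the logistic p-value stays conservative.

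**The case against.** The strongest reply is that the protocol never says pooled or equal-variance. Student's t-test is often used as a generic name. As a matter of general software knowledge, not stated in the protocol, R's t-test function applies the Welch form unless pooling is requested. The variance option could also be settled in an analysis plan that is not shown. This stands in part: pooling is not established. But the protocol does name a test, and in its standard meaning that test is the pooled one. If Welch is intended, the wording misdescribes it; if pooling is intended, the level is unprotected. The same edit serves both cases.

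The second reply is that the SD ratios have no source in the document. This stands in full. A reader might infer that patients with events are more variable and that the tests are therefore too liberal. Nothing in the protocol supports that direction, and at equal SDs there is no error at all.

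The third concerns scope, and it also stands. A reader might extend the point to every continuous variable, but those not judged normal go to the Mann-Whitney test. A reader might also extend it to operating room against non-operating-room patients, where the suggested 40 and 10 per centre give 4:1. At 2,000 against 8,000 the pooled level would be 2.5%, 7.9% and 12.1% at ratios of 0.8, 1.2 and 1.5. However, the primary outcome is binary, no t-tested endpoint is named for that comparison, and the split is a suggestion rather than a fixed ratio.

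The fourth is that real predictors would seldom be lost. At a ratio of 0.7, a true difference of 0.10 SD (of the non-event group) has 93% power with the pooled test and 98% with Welch. Only differences near 0.05 SD suffer materially (29% against 53%). That is fair, and it keeps the point minor.

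**Conclusion.** The point holds as a conditional and minor one. If the named test is the usual pooled-variance test, its nominal 5% level is not protected in the planned comparison of about 1,000 against 9,000 patients. Over assumed SD ratios of 0.8 to 1.5 the actual level runs from 1.9% to 15.4%, and it is exact at equal SDs. This rests on the planned event rate being met, on the variable being analysed as normal, and on SD ratios that the protocol does not supply.

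A reader might conclude that the trial's significance level has been shown to fail, or that its main result is compromised. Neither follows. The variance assumption is not stated and the SDs are unknown. The primary aim is an incidence, which uses no t-test. The effect is confined to descriptive comparisons and, if the same tests are applied there, to the screen before the logistic model.

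**What to change.** In both the synopsis and the Statistical Analysis section, replace the reference to Student's t-test with the Welch (unequal-variance) t-test, and report each mean difference with its Welch confidence interval.

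The cost is one phrase in two places. With groups this large, the loss of efficiency if the SDs turn out equal is negligible. The change needs no further data and leaves the sample size untouched.

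Its reach should be stated honestly. It keeps the descriptive comparisons at their nominal level and limits false entry into the model when the event group has the larger SD. It does not by itself correct the model-based logistic p-values when that group has the smaller SD.

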The project will be presented and a call for centres will be announced during international meetings of anesthesiology.

We will also apply for receiving the endorsement of international scientific societies in order to promote and enhance participation to this study.

PATIENTS RECRUITMENT

After obtaining the local approval, each center will select a start date and screening for patients' eligibility will start. In order to avoid selection bias while addressing study feasibility and balance across different participating centers, a maximum number of 50 patients from each center will be enrolled. To maintain data collection feasible, optimize enrolment of all consecutive patients, especially for high-volume centers, and balance number of enrolled patients across different centers, we suggest to focus screening for enrolment from a pre-defined number of operating rooms (3 to 5 according to local workload) up to the final enrollment of 40 patients/center in the anesthesia setting without any time limitation. All consecutive patients undergoing advanced airway management in the NORA setting will be screened up to the final enrollment of 10 patients/center without any time limitation. Local investigators will be involved in the screening of operating list of those selected areas.

Screening of all consecutive patients will involve all patients treated in the selected areas of each center. Screening and reporting of all consecutive treated patients will be interrupted only when the target number of patients/center will be reached.

PUBLICATION AND AUTHORSHIP POLICY

The main results of STARGATE study will be published in a peer—reviewed international medical journal. Authorship policy will follow the International Committee of Medical Journal Editors (ICMJE) recommendations. Authorship will be considered based on contributions to recruitment of patients, data acquisition and cleaning, analysis and interpretation of the data, manuscript writing, submission of national/local grants AND final approval of the version to be published AND agreement to be accountable for all aspects of the work, in ensuring that questions related to the accuracy or integrity of any part of the work are appropriately investigated and resolved.

Dipartimento Oncologia

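### The named tests and the logistic model ignore clustering by centre (210 centres, up to 50 patients each), so p-values for exposures that vary between centres will be too small

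*Protocol*

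**What the plan says.** The protocol's STATISTICAL ANALYSIS section, and the same text in the synopsis, names the methods one by one. For continuous variables: "We will report mean and standard deviation of normally distributed variables and we will compare them using the student T-test", and for non-normal ones, "comparing them using the Mann-Whitney U test". For categorical variables: "Categorical variables will be expressed as proportion and compared using the Chi-square or Fisher exact test as appropriate".

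Risk factors are then sought in two steps. First: "We will perform a bivariate analysis to identify variables associated with the composite outcome of major peri-intubation adverse events". Second: "significant variables will be then used to construct a multivariate logistic model in order to identify independent variables". The threshold is stated: "A two-sided p-value < 0.05 will be considered statistically significant".

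On the design, the Sample size section says "we plan to recruit a total number of 210 centres", and PATIENTS RECRUITMENT says "a maximum number of 50 patients from each center will be enrolled", with a suggested split of 40 patients in the operating room and 10 in NORA. CENTRES RECRUITMENT opens the study to academic and non-academic hospitals worldwide and says that centre characteristics will be collected.

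The protocol mentions no centre or country effect, GEE, robust variance, ICC or design effect. It also specifies no confidence interval, including for the primary incidence.

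**The concern.** In their ordinary form, all the named methods treat each patient as an independent observation. The protocol itself gives reasons to expect correlation within a centre:

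- One component of the primary outcome is unplanned vasopressor use or a fluid load to hold a target pressure. No target value is set, so this depends on local practice.
- Appendix 2 leaves the interval between non-invasive pressure readings to clinical practice, which affects how often hypotension is detected.
- Screening within a centre is suggested from only 3 to 5 operating rooms.

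When an exposure also varies between centres, the naive standard error is too small. Propofol versus another hypnotic is a planned comparison that plausibly follows centre habit, and type of surgery may do so too. Because significance in the bivariate screen decides what enters the logistic model, the error carries into the list of factors reported as independent. A plain binomial interval around the headline incidence would also overstate its precision.

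**Working it through.** **Reproducing the stated sample size.** Sample size section: 1000 events / 0.10 = 10,000. Adding 5% gives 10,000 × 1.05 = 10,500, and 10,500 / 50 = 210 centres. The figures reproduce, so they contain no allowance for clustering.

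**Inputs.** From the protocol: N = 10,500, K = 210 centres, m = 50 (a maximum, but 210 centres yield 10,500 only if every centre reaches it), incidence p = 0.10, two-sided 5%. Assumed, because the documents give no value: a normal centre effect on the log-odds scale with SD 0.42, 0.75 or 1.1, and the intercept chosen so that the marginal incidence stays at 10%. Numerical integration converts these SDs to observed-scale ICCs of 0.016, 0.052 and 0.110.

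**Precision of the incidence.** Naive half-width = 1.96 × √(0.10 × 0.90 / 10,500) = 0.57 points. Design effect DE = 1 + (m − 1) × ICC. Clustered half-width = 0.57 × √DE. Coverage of a naive 95% interval = 2Φ(1.96/√DE) − 1.

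| Centre SD | ICC | DE | Effective N | 95% half-width | Naive coverage |
|---|---|---|---|---|---|
| 0.42 | 0.016 | 1.8 | about 5,850 | 0.77 points | 86% |
| 0.75 | 0.052 | 3.6 | about 2,940 | 1.08 points | 70% |
| 1.1 | 0.110 | 6.4 | about 1,640 | 1.45 points | 56% |

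For a smaller ICC of 0.01: DE = 1 + 49 × 0.01 = 1.49, half-width 0.70 points, coverage 89%. With ICC = 0 nothing changes.

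**Type I error of the unadjusted chi-square test at nominal 5%.** The variance of the difference is multiplied by a factor f that depends on how the exposure is spread over centres, and the true error is 2 × [1 − Φ(1.96/√f)].

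- *Centre-level exposure* (for example academic versus non-academic, if tested): f = DE. This gives 14%, 30% and 44%. Simulation of 210 × 50 patients gives 14%, 30% and 44% to 45%.
- *Practice-type exposure* (for example choice of hypnotic; covariate ICC assumed 0.3): f ≈ 1 + 49 × ICC × 0.3 = 1.24, 1.77 and 2.62. This gives 8%, 14% and 23%. Simulation gives 8%, 14% and 21% to 22%.
- *OR versus NORA*, 40:10 in every centre: f ≈ 1 − ICC = 0.98, 0.95 and 0.89. This gives 4.8%, 4.4% and 3.8%. Simulation runs from about 5% down to 3.4%.

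**The case against.** The strongest reply has four parts.

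*The primary aim is descriptive.* With roughly equal centre sizes, clustering alone does not bias the pooled proportion, and 10% ± 1.5 points is still informative. The sample size is justified by an event count for modelling, so the missing design effect breaks no stated precision target. This stands, and it is why no extra patients are called for.

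*No interval is specified, and a SAP may exist.* A reader might infer that the protocol's confidence intervals are wrong. The document does not support that, because it plans none. All that can be said is that a simple binomial interval, if used, would be too narrow. The tests and the model are different: they are named in the protocol. A SAP that corrected them would then disagree with the protocol.

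*Not every test is anti-conservative.* A reader might infer that all p-values are too small. OR versus NORA, the first listed secondary comparison, is about nominal or slightly conservative. ASA, BMI, urgency and difficult airway are patient-level comparisons, and the effect on them depends on how they are spread over centres, which the documents do not say. None of the listed comparisons is purely centre-level, so the 14% to 45% range applies only if centre characteristics are tested.

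*The size rests on an assumed ICC.* True. Design effects above 7 or half-widths near 1.7 points would need an incidence above 10% at the SDs used here, so they are not claimed.

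**Conclusion.** The concern holds for the named tests, the significance-based screen and the plain logistic model, wherever the exposure varies between centres. Under an assumed observed-scale ICC of 0.016 to 0.11, 10% incidence and full recruitment of 210 × 50, the design effect for the overall incidence is about 1.8 to 6.4. The nominal 5% error becomes about 8% to 22% for a practice-type exposure with covariate ICC 0.3, and about 14% to 45% for a centre-level exposure. Even at ICC 0.01 the centre-level error is about 11%.

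The finding does not extend to the point estimate of incidence, to OR versus NORA as a source of false positives, or to the planned number of patients.

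**What to change.** In STATISTICAL ANALYSIS, and in the matching synopsis text, state that:

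1. the primary incidence is reported with a 95% confidence interval that allows for clustering by centre;
2. the bivariate screen, the planned secondary comparisons and the multivariable model use a logistic model with a random intercept for centre, or GEE or cluster-robust variance by centre;
3. the ICC of the primary outcome is reported.

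The plain t, Mann-Whitney and chi-square or Fisher tests may stay for descriptive tables, but should not decide which variables enter the model or which associations are claimed. Nesting centre within country is optional.

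The cost is a few sentences and standard R methods, with no extra patients and no design change. Centre should already be identifiable, because enrolment is counted per centre. The price is a wider interval around the headline incidence and probably fewer significant associations among exposures that follow centre practice.

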Data will be collected real-time by an investigator not involved in airway management using either the paper or the electronic version of the case report form on the Redcap.

The following variables will be collected:

- Informed consent and admission data
- Demographic and clinical characteristics
- Type of procedure (time, setting, type of surgery, elective or emergency

- Airway evaluation (anticipated difficult airway management)
- Monitoring applied during the procedure
- Ongoing respiratory and hemodynamical support before intubation
- Patient's parameters
- Preoxygenation method and use of apnoeic oxygenation (position during preoxygenation, rapid sequence induction applied)
- Fraction of expired O₂ (FeO₂) at the end of preoxygenation
- Application of any apnoeic oxygenation method
- Application of rapid sequence induction intubation
- Drugs used for induction (molecules and doses)
- Elective method for advanced airway management
- Operator's characteristics
- Method used for the second (and following) attempt
- Method used for adequate tube placement confirmation
- Duration of airway management procedure
- Outcome of endotracheal intubation (total number of attempts, laryngoscopic view, minimum SpO₂ during laryngoscopy, need for LMA)
- Advanced airway management-related complications (severe cardiovascular collapse, severe and mild hypoxemia, cardiac arrest, airway injury or any bleeding, aspiration of gastric contents, dental injury, emergency front of neck airway (FONA), cannot intubate cannot oxygenate scenario (CICO), unplanned need for ICU secondary to airway management complications)
- Extubation procedure
- In-hospital mortality

Local investigators are expected to transfer all collected data into an electronic CRF (eCRF, Research Electronic Data Capture – RedCap). Each local investigator will be trained on how to use the eCRF and will receive a personalized username and password. Each patient will be coded through a patient identification number generated by the eCRF and no patient names or initials will be present on the paper CRF.

Data will be handled confidentially and the paper CRF will be stored behind a lock at each local site. Any source of information which may allow to link a record with a patient will be destroyed at the end of the monitoring phase.

STATISTICAL ANALYSIS

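### The multivariable model is built by bivariate significance from an undefined candidate pool, with nothing to keep out fields that define or follow the outcome

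*Protocol*

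**What the plan says.** The Statistical Analysis section of the protocol, repeated in the synopsis, gives a two-step rule. First, "We will perform a bivariate analysis to identify variables associated with the composite outcome of major peri-intubation adverse events". Then, "significant variables will be then used to construct a multivariate logistic model in order to identify independent variables". The only threshold is the general one: "A two-sided p-value < 0.05 will be considered statistically significant". No other criterion for entering the model is given.

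The Sample size paragraph starts from "Post-intubation hypotension has been reported in up to 10% of patients". It aims for 1000 events so that ten or more candidate factors can be studied, but does not name those factors.

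The only list of variables is under Data Collection. It mixes three kinds:
- fields known before induction, such as demographics, airway evaluation, and respiratory and haemodynamic support before intubation;
- fields that arise during the procedure, such as "Duration of airway management procedure" and "Outcome of endotracheal intubation (total number of attempts, laryngoscopic view", the latter item continuing with the lowest SpO₂ at laryngoscopy;
- fields that are complications or come later, including cardiovascular collapse, hypoxaemia, cardiac arrest, extubation and in-hospital mortality.

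The planned secondary analyses include "Airway management procedure: difficult airway management vs not difficult" and "Type of hypnotic drug used: propofol vs different drug".

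**The concern.** Selection on marginal p-values is a weak way to find independent predictors. A confounder whose marginal association is cancelled by a correlated factor is dropped although it matters jointly. A weak or uncommon factor is kept or lost largely by chance. The final p-values take no account of the selection.

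The second difficulty is timing. The rule puts no limit on when a candidate must be known. SpO₂ below 80% is a component of the primary outcome, so a lowest SpO₂ below 80% at laryngoscopy, inside the outcome window, is the event itself. Such a field would pass any significance screen and take over the explanation from factors known before induction.

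At stake is the reading of the model that the 1000-event target was chosen to support. The incidence estimate, which is the primary aim, does not depend on it.

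**Working it through.** **1. The plan's own figure.** Inputs from the Sample size paragraph: 1000 events, 10% event rate, 5% loss, 50 patients per centre.
- 1000 / 0.10 = 10,000 patients.
- 10,000 × 1.05 = 10,500, the stated total (10,000 / 0.95 = 10,527 by the usual formula, a trivial difference).
- 10,500 / 50 = 210 centres. The figures reproduce.

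**2. Is screening needed?** Events per variable = events / number of variables.
- 1000 / 10 = 100; 1000 / 30 = 33; 1000 / 60 = 17.
- After 5% loss from 10,500: 9975 × 0.10 = 997.5 events, and 997.5 / 10 = 99.75.
- If the event rate were 5% or 2% (assumptions), ten variables would have 500 / 10 = 50 or 200 / 10 = 20 events each.

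At the planned size, ten or more variables can all be entered.

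**3. What the screen lets in by chance.** For k independent null candidates (k is assumed, because the pool is undefined), the expected number passing is 0.05k, and P(at least one) = 1 − 0.95^k.
- k = 10: 0.5 and 0.40.
- k = 30: 1.5 and 0.79.
- k = 60: 3 and 0.95.

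**4. What the screen misses.** Power of a two-sided 0.05 comparison of two proportions, 10,000 patients, 10% event rate in the unexposed:
- prevalence 5%: 0.26 for an odds ratio of 1.2, 0.48 for 1.3, 0.84 for 1.5;
- prevalence 10%: 0.42 for 1.2, 0.72 for 1.3;
- prevalence 50%: 0.81 for 1.2, 0.985 for 1.3.

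**5. Joint confounders.** Take two standardised normal factors with log odds ratios b₁ = ln 1.5 = 0.405 and b₂ = ln 1.2 = 0.182 and correlation ρ. The marginal association of the second is zero when b₂ + ρb₁ = 0, that is ρ = −0.182 / 0.405 = −0.45. The screen then drops it except by chance, and the first factor's coefficient becomes about 0.405 − 0.45 × 0.182 = 0.323, an odds ratio of about 1.38 instead of 1.50. This is an illustration of the mechanism. Exact cancellation is a special case.

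**6. Instability at the planned size.** Simulation with assumed inputs: 30 candidates (10 real, 20 null), pairwise correlation 0.1, 10,000 patients, about 970 events, 150 runs.
- Real odds ratios per SD of 1.2 or more were significant in the final model in essentially all runs, 1.15 in about 95%, 1.1 in 73%.
- Mean odds ratios when retained: 1.1 became 1.12 to 1.13; 1.5 stayed 1.50.
- The screen passed nearly every null variable, because each was correlated with real ones, so it filtered almost nothing. About 5% of nulls (1 of 20) were significant in the final model.
- With about 97 events, the same procedure retained an odds ratio of 1.2 in 21 to 28% of runs, inflated to 1.35 to 1.37.

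**7. Masking.** Simulation with assumed inputs: 10,000 patients, about 10% events, 8% with a baseline airway factor, more than two attempts in 20% of those with it and 3% of those without, 30 runs per row. Severe hypoxia is the lower tail of the simulated saturation, sized to the stated share of events.

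| Hypoxia share of events | OR of baseline factor alone (detected) | OR after adding minimum SpO₂ and attempts (detected) |
|---|---|---|
| 5% | 1.24 (50%) | 1.10 (10%) |
| 10% | 1.30 (73%) | 1.07 (0%) |
| 20% | 1.57 (93%) | 1.14 (17%) |
| 40% | 1.86 (100%) | 1.09 (10%) |

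Minimum SpO₂ was significant in every run. The two variables were added together, so part of the fall is mediation through attempts and not circularity.

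**The case against.** The strongest reply is that the Data Collection list is not a predictor list. Taken as one, it would admit consent data and mortality, which nobody intends. The reference to ten or more candidate factors suggests a clinically chosen set, and a candidate list may sit in a statistical analysis plan that is not at hand. This stands in part. A reader might infer that the pool includes minimum SpO₂ and the complication fields; the protocol shows only that the pool is undefined and that nothing excludes them. The entry rule itself, however, is stated in the protocol, and an analysis plan that follows the protocol would carry it out.

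A reader might also infer that the selected predictors will be generally unstable and their coefficients overstated. Steps 2 and 6 do not support that at about 1000 events. The trouble is confined to weak or rare factors, unless events fall far below plan or the pool is very large.

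Nor are number of attempts and airway difficulty circular in the way that minimum SpO₂ is. The Rationale treats first-pass failure as raising the risk, so they are partly mediators and a legitimate question. They still need separate handling: a difficult procedure, by number of attempts, is listed under Other Outcomes, and Appendix 1 defines difficult intubation by more than two laryngoscopy attempts, so the difficulty comparison may use a factor known only after induction. Duration runs from preoxygenation to confirmed placement, so it too overlaps the outcome window, although part of it precedes induction.

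Finally, the propofol comparison is a planned secondary analysis with no causal claim, and leaving its adjustment set to an analysis plan is not an error. What remains is that if it is adjusted through this model, a confounder stays only if it passes the screen.

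**Conclusion.** The point holds in a limited form and should be acted on. Bivariate significance is the sole stated route into a model meant to identify independent factors, the candidate pool is undefined, and no text keeps out fields that define or follow the event. That minimum SpO₂ below 80% at laryngoscopy coincides with an outcome component follows from the protocol's own definitions and needs no assumption.

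The size of the harm does rest on assumptions. The masking results depend on assumed effect sizes and hypoxia shares, the screen's power on a 10% event rate and chosen prevalences, and the chance inclusions on an assumed number of independent candidates. All calculations treat patients as independent. They show direction and plausible scale, not a forecast for this study. The documents do not support calling the whole model unstable or uninterpretable, and the incidence estimate is not touched.

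**What to change.** Replace the screening sentence, in the Statistical Analysis section and the synopsis, with a covariate set chosen on clinical grounds, fixed before data lock, limited to information known up to induction and entered in full. Examples are age, sex, BMI, ASA class, urgency, place, type of surgery, respiratory and haemodynamic support before intubation, anticipated difficulty, preoxygenation and induction drugs.

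State that outcome-defining and post-event fields (minimum SpO₂ at laryngoscopy, the complication fields, extubation, in-hospital mortality) are not candidates. Report intra-procedural factors (attempts, difficulty, duration) in a separate model labelled as such. Estimate the hypnotic, place and urgency comparisons from the pre-induction adjusted model.

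The cost is wording. The headings under Data Collection and the planned secondary analyses already cover these variables, and the sample size stays at 10,500. The downside is that the list must be agreed in advance.
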